***Additional Inclusion Criteria Aim 2:**

- 8) Able to present for baseline and follow up in person,
- 9) Unexposed to a GLP-1 agonist in the past year,
- 10) Starting on a GLP-1 agonist in the next <6 months,
- 11) Plan to be exposed to GLP-1 agonist for a minimum of 72 weeks following enrollment.

Participant Population(s)

Accrual Number:	Category/Group:	Consented/Enrolled:
Local	Individuals with MS already treated with Ocrelizumab and GLP-1 agonist	60
	Ocrelizumab-treated MS patients initiating GLP-1 agonist	40
Study-wide		
Total:		100

RECRUITMENT METHODS:

Potential participants will be identified through online research advertising webpages (e.g., ClinicalTrials.gov, Northwestern's clinical trials website), the investigator's connections with MS neurologists in the practice and surrounding practices, advertisements in MS clinics, the National MS Society local chapter's and national websites, MS physician networks, social media directly to patients, flyers in the medical infusion center, weight loss and nutrition clinics in the region, and through clinic newsletters and the word of mouth.

Interested patients will be screened through an online RedCap™ form for the study's eligibility criteria. Medical records review will occur by the investigators to ensure the criteria are met. Participants will then be called by telephone or met in person to describe the study procedures in detail.

CONSENT PROCEDURES:

Consent will be taken by a trained study team research coordinator or physician. All consent will be written on a standardized consent form, in English. Consent may be performed electronically using REDCap e-sign with an institutionally approved account. Participants will be given >24 hours to review the consent form and provide consent. Given the complexity of the study tasks including multiple self-reported variables, only participants who are able to provide their own consent will be enrolled.

Vulnerable Populations

Vulnerable populations will not be enrolled. Participants who lack capacity to voluntarily consent (e.g. institutionalized, dementia) are excluded as per the criteria listed above.

STUDY PROCEDURES:

Aim 1 will allow fully remote participation, drawing from geographically diverse settings throughout the USA. Participants in Aim 1 do not need to visit the study site in person or be

independently mobile but must be continuously available during the study timeframe remotely for PROMs and study surveys and calls.

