Participants who discontinue GLP-1 agonist drugs for any reason, including tolerability, cost, desired weight loss outcome, etc., will continue to be observed until the end of the study period. It is possible that participants will have periods of discontinuation and then resume GLP-1 agonist treatment. The participant will be observed until (a) week 72 visit (i.e. end of study period), (b) participant withdrawal with no consent to continue monitoring, or (c) investigator-decided withdrawal of a participant from the study (e.g. severe medical illness preventing study completion, departure far from study site, etc.).

Participant Compensation for Involvement in Research Procedures

Aim 1: Each participant will receive 75 USD every 3 months with a total of up to **600 USD**.

Aim 2: Each participant will receive 150 USD at baseline and 100 USD every subsequent visit occasions and then 150 USD at the final study visit with a total of up to **500 USD**.

Participants will have the option to receive cash or a gift card. Participants who receive cash will need to provide their social security number for the reporting of taxable income to the Internal Revenue Service, according to applicable laws.

There is no anticipated drug development or future product anticipated in this study. A study participant will not have any right to compensation or ownership interest related to such development.

RISKS AND BENEFITS:

Risks to Participants

Participants in this study may have side effects of the medications under investigation including both Ocrelizumab and the GLP-1 medication, although these will be given in the context of clinical care for U.S. Food and Drug Administration (FDA)-approved indications. In particular, the GLP-1 class of medications is known to cause gastrointestinal symptoms, including nausea, vomiting, early satiety, and abdominal discomfort. These are considered reversible, common (approximately 1/3 of all people treated with a GLP-1 medication), and expected. These risks are often mild to moderate and in some cases may lead to early discontinuation of the medication if poorly tolerated. Participants may experience injection-site reactions which could be bothersome.

An additional risk is that participants will be psychologically burdened by repeated testing and surveying throughout the study; however, no clinical harm is anticipated from surveys or the clinical assessments done during the study procedures.

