Variables of interest will be reported using descriptive frequency-based statistics (e.g. mean, median, range). Subgroups of interest (e.g. by gender, disability level below or above the median, etc.) will be compared using t-tests and tests of two proportions as appropriate. Repeated measures (e.g. weight) will be graphed and displayed. Change in values will be reported (final minus starting weight). If needed to report an outcome, repeated measures analyses, will be made using generalized linear models. Incidence of tolerability issues will be reported as the number of events per number of person-months of observation available.

Aim 2:

This will be an intention to treat analysis. All participants who enroll in the single-arm study will be analyzed to the end of their study participation, either the end of the planned study period or time of withdrawal. Data will be analyzed in aggregate with descriptive subgroup analyses performed with the following variables and subgroupings of interest: (1) sex at birth, (2) age at enrollment below or above the median age, (3) duration of GLP-1 (72 weeks versus early discontinuation), (4) BMI group (<30.0 kg/m², 30-39.9 kg/m², >40.0 kg/m², and (5) EDSS score at enrollment above or below the median.

The primary outcome measure is PIRA, dichotomized as present or not, as measured by the rater-determined composite functional outcomes score. This includes the EDSS score with contributions by the 9-hole peg test, SDMT, and 25-foot walking test, and will be constructed as presented in the ORATORIO trial for Ocrelizumab in primary progressive MS vs. placebo.

EDSS will be measured pre-GLP-1 (enrollment) and at the participant's end of study (i.e. one of (a) the end of planned study enrollment period, (b) administrative withdrawal, or (c) participant withdrawal). A positive change in EDSS score of 1.0 points with a baseline EDSS of <5.0 or a positive change in EDSS score of 0.5 points or more with a baseline EDSS score of 5.0 or higher will be considered PIRA. EDSS will be captured at each study visit but the first and last EDSS scores will contribute to the assessment of PIRA for the primary study outcome's hypothesis testing. The use of the EDSS scores at each q24week study visit will also be used in a generalized linear model to determine disability level worsening at any timepoint.

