The submission of ethics board approvals will take approximately 4 months and will be submitted by no later than June 30, 2025. The anticipated start date of the study will be September 15, 2025. Recruitment processes for both study participant groups (Aims 1 and 2) will occur simultaneously. The first patient in for Aim 1 is anticipated within 30 days and the first in for aim 2 is anticipated within 60 days of study start. Recruitment will continue until the target participant enrollment number is reached in both study groups. The enrollment pace will be set not to exceed 6 people per month for Aim 1 to ensure study procedures are robust, with a target of 4-6 people per month. Aim 1 will take approximately 12-15 months to enroll. The anticipated time to complete the enrollment of Aim 1 is December 31, 2026. Aim 2 will take an estimated 12 (up to 18) months to enroll with an anticipated enrollment of 3-4 participants per month. Aim

2 will also complete enrollment in approximately December 2026. Each participant will be followed for 72 weeks. It is anticipated that the last participant out (Aim 2, and complete study) will be April 2028. The final data cleaning and analysis will take approximately 4 months. Interim results will be available to the sponsor at defined intervals before the final study report, at approximately every 6-month intervals. The final study results will be compiled into reports and manuscripts by spring 2028 with study closure in approximately summer 2028.

Qualifications to Conduct Research and Resources Available

The Principal Investigator is a board-certified neurologist with a PhD in International Health Epidemiology. She has over 11 years of experience in neuroimmunology and has served as the lead investigator on multiple clinical trials and observational studies focused on multiple sclerosis.

The research team includes trained clinical research staff who have completed all required certifications, including Good Clinical Practice (GCP), CITI Program training, and other protocol-specific qualifications relevant to this study. All study personnel will receive thorough training on the study protocol, the informed consent process, and ethical considerations to ensure the safety of the participants.

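### The Aim 2 subgroup on GLP-1 duration is defined after baseline, and its two categories do not fit the trial's own 72-week clock

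*Protocol*

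**What the plan says.** The Aim 2 analysis text, under Data Management and Confidentiality, plans "descriptive subgroup analyses performed with the following variables and subgroupings of interest" and lists five. The third is "duration of GLP-1 (72 weeks versus early discontinuation". The others are sex at birth, age at enrolment, BMI group and EDSS at enrolment. The same text sets the analysis population: "All participants who enroll in the single-arm study will be analyzed to the end of their study participation", meaning week 72 or withdrawal. Baseline EDSS is taken at enrolment before GLP-1, and PIRA compares the first EDSS with the last.

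Three of the Additional Inclusion Criteria for Aim 2 fix the exposure window:

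- "Unexposed to a GLP-1 agonist in the past year"
- "Starting on a GLP-1 agonist in the next <6 months"
- "Plan to be exposed to GLP-1 agonist for a minimum of 72 weeks following enrollment"

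Study Timeline gives the follow-up: "Each participant will be followed for 72 weeks". The section on study withdrawal keeps people who stop GLP-1 under observation to the end of the study, and adds: "It is possible that participants will have periods of discontinuation and then resume GLP-1 agonist treatment". The Study Aims section, by contrast, speaks of two years of monitoring for Aim 2.

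**The concern.** A subgroup should sort people by something known at the start. This one sorts them by how long they went on taking the drug, which depends on events during the same period in which the outcome develops. The listed reasons for stopping include intercurrent illness, intolerance, patient preference and reaching the weight target. Several of these are plausibly linked to prognosis, and worsening MS could itself lead to stopping through preference or the open-ended last reason.

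The categories also do not match the cohort that the eligibility criteria create. Follow-up starts at enrolment, but the drug may start months later, may be interrupted, or may never start, since the study does not supply it.

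At stake is how one table would be read. The protocol states that there is no comparison group, and GLP-1 exposure is not among the variables listed for the PIRA regressions. This split is therefore the only stated within-study contrast by GLP-1 exposure. The benefits section looks ahead to a finding that GLP-1 agonists protect against PIRA, so readers may turn to this contrast for support that it cannot give.

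**Working it through.** **Inputs.** Follow-up: 72 weeks from enrolment (Study Timeline; also the endpoint text, Table 2 and the withdrawal section). Start lag: 0 to just under 6 months, or 26 weeks (Aim 2 inclusion criteria). Exposure at entry: none in the past year. Aim 2 size: 40. The 72 weeks in the subgroup label is a category threshold, so there is no calculated figure to reproduce.

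**Step 1: longest attainable exposure.** Maximum weeks on GLP-1 = follow-up − start lag, with 1 month = 52/12 = 4.33 weeks.

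| Start lag | 72-week follow-up | 2-year (104-week) follow-up |
|---|---|---|
| 0 | 72 | 104 |
| 1 month | 72 − 4.3 = 67.7 | 99.7 |
| 3 months | 72 − 13 = 59 | 91 |
| nearly 6 months | just over 72 − 26 = 46 | just over 78 |

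On the 72-week clock, a full 72 weeks requires a start on the day of enrolment. On the two-year clock, everyone could reach it.

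**Step 2: how many might come close.** The protocol gives no distribution of start lags. Assuming a uniform lag, and nobody stopping, to show a range:

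| Lag uniform over | Mean exposure (weeks) | At least 71 weeks | At least 68 weeks |
|---|---|---|---|
| 0–4 weeks | 72 − 2 = 70 | 1/4 = 25% (10 of 40) | 100% (40 of 40) |
| 0–13 weeks | 72 − 6.5 = 65.5 | 1/13 = 8% (about 3 of 40) | 4/13 = 31% (about 12 of 40) |
| 0–26 weeks | 72 − 13 = 59 | 1/26 = 4% (about 1.5 of 40) | 4/26 = 15% (about 6 of 40) |

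The share near 72 weeks thus depends heavily on the lag and on any tolerance allowed.

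**Step 3: who fits where.**

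| Participant | Literal duration | On drug through week 72 |
|---|---|---|
| Starts in month 3, never stops | neither: 59 weeks, no discontinuation | first group |
| Stops, then resumes | neither is defined for this case | unclear |
| Never starts | neither | neither |
| Stops for good | early discontinuation | early discontinuation |

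The second reading makes the first group reachable, but that group then mixes exposures of about 46 to 72 weeks under a label that says duration.

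**Step 4: observation time.** Someone who leaves the study early cannot be in the 72-week group, and the last EDSS comes early. As an illustration, assume a constant hazard with 24% PIRA at week 72 (24% is the upper published figure in the sample size text). Expected PIRA by week t is 1 − 0.76^(t/72):

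- Week 24: 1 − 0.76^(1/3) = 8.7%
- Week 48: 1 − 0.76^(2/3) = 16.7%
- Week 72: 24%

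A difference of this kind would arise from time observed alone. It does not apply to people who stop the drug and stay in follow-up.

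**The case against.** The best defence is that the label was meant as on treatment to week 72 versus stopped early. The inclusion criterion on planned exposure counts its 72 weeks from enrolment, and the withdrawal section treats the week 72 visit as the end of the study. On that reading the first group is reachable. The analysis is also called descriptive, no test is attached to it, and detailed rules for interruptions often belong in a statistical analysis plan.

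Much of this stands, and it rules out three stronger readings that a reader might infer:

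- **That every late starter is counted as an early discontinuation.** The protocol does not say so. The second category is early discontinuation, not fewer than 72 weeks, so a continuous late starter is unplaced rather than assigned to it.
- **That the 72-week group is empty or nearly so.** This needs strict counting of duration, the 72-week clock and real start lags. The lag distribution is unknown, part of the lag may pass between screening and baseline, and the two-year statement would let everyone reach 72 weeks.
- **That stopping the drug shortens observation.** People who stop are followed to week 72. Only study withdrawals have less time.

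The defence does not remove the conflict. The protocol itself fixes the two categories, and they clash with its own start window and its own expectation of stop-and-resume use. Calling the analysis descriptive does not turn a post-baseline split into a baseline subgroup.

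**Conclusion.** The concern holds as a problem of definition and interpretation. The subgroup depends on behaviour after baseline. Read literally, it leaves out continuous late starters, interrupters and never-starters; read generously, it pools about 46 to 72 weeks of exposure. A PIRA contrast across it is open to selection and reverse causation and, among study withdrawals only, to shorter follow-up.

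The exposure limits assume 72 weeks of follow-up from enrolment, as most of the protocol states. The uniform lags and constant hazard are illustrations, not figures from the protocol. Reverse causation is a possibility that the design leaves open; the protocol offers no evidence of its size. The primary analysis takes all enrolled Aim 2 participants and does not use this split, so it is not affected. The change is worth making, but the study does not depend on it.

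**What to change.** Replace the split with GLP-1 exposure accrued before each visit: cumulative weeks on drug counted from the actual start, taken from the medication review and adherence questionnaire in Table 2. Enter it as a time-varying term in the 24-weekly EDSS model already planned, alongside time since enrolment so that exposure does not simply stand in for elapsed time. Do not use a landmark at week 24. It falls inside the permitted start window, so people not yet started would be grouped with people who had stopped.

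If a descriptive table is kept, count exposure from the actual start and give four rows: continuous to end of study, stopped, interrupted and resumed, and never started. Show follow-up time for each row, and state that the table does not support a causal conclusion about GLP-1 and PIRA.

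The 72-week and two-year follow-up statements for Aim 2 must also be reconciled, because the attainable exposure depends on which applies.

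The cost is a few lines of text and slightly more analysis, with no new data. With 40 participants and three scheduled post-baseline visits the estimate will be imprecise. Measuring exposure before each EDSS reduces reverse causation but does not remove it.

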- (2) Enroll a single-arm, open-label trial of **40** Ocrelizumab-treated MS patients who are soon starting GLP-1 agonists, monitored prospectively for 2 years to measure MS **progression** (clinical disability worsening, stability or improvement) every 3 months, including (a) clinical assessments (e.g. EDSS, 25-foot timed walk, SDMT) as used in the ORATORIO trial of Ocrelizumab, (b) PROMs on progression in MS including fatigue, ambulation distance, mood; and (3) simple objective biomarkers of disease (e.g. plasma neurofilament light chain, glial fibrillary acidic protein).

Overview: Aims 1 and 2 will recruit participants simultaneously but draw upon MS participants at different points in their GLP-1 agonist treatment. Participants can enroll in either the cohort of Aim 1 (in-person or remote) or the open label trial of Aim 2 (in-person only), not both aims. All participants will be Ocrelizumab-treated for MS upon study enrollment.

Study Endpoints

The primary outcome measure is **PIRA** (progression independent of relapse activity), based primarily on clinical assessment, dichotomized as present or not.¹²

For Aim 1, the cohort, patient-derived disability status (PDDS) score, and ambulation score (self-reported) will be the primary endpoints of interest.

For Aim 2, the clinical trial, PIRA will be measured pre-GLP-1 start and at study end (week 72). A composite score of disability, similar to the ORATORIO¹³ trial will be constructed including EDSS score, 25-foot timed walk, 9-hole peg test, and SDMT score.

Study Interventions/ Investigational Agent

Glucagon-like peptide-1 agonist agent is the study agent of interest. This study will not supply the GLP-1 drug but depend on the patient's clinical prescription of this drug. Similarly, all participants will be treated with Ocrelizumab for the indication of MS; however, the study will not provide Ocrelizumab as it will be part of the participant's routine clinical care.

Study Procedures

Inclusion Criteria, Aims 1 and 2:

- 1) Diagnosis of MS (2019 revised McDonald criteria) of any type (PPMS, RRMS, SPMS) by a neurologist,
- 2) Adult age 18-70 years,
- 3) BMI $\geq 24.0 \text{ kg/m}^2$,
- 4) Taken at least one dose of Ocrelizumab prior to study entry,
- 5) EDSS < 7.0 ,
- 6) Able to provide individual informed consent,
- 7) MRI available to confirm the diagnosis of MS.

Exclusion Criteria, Aims 1 and 2:

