- 1) Prior exposure to Mavenclad, Lemtrada, Cyclophosphamide, stem cell transplant or related bone marrow suppressive treatment,
- 2) Current clinical trial participant,
- 3) Unable to speak a language for which translation can be found in the hospital system,
- 4) Unclear documentation of MS diagnosis or prior or current MS treatment,
- 5) Relapse within the past 3 months,
- 6) Recent major surgical procedure in the past 6 months,
- 7) Exposure to steroids (systemic) within the past 3 months,
- 8) Not on Ocrelizumab in the past > 9 months,
- 9) Moribund status,
- 10) Underweight or experiencing protein malnutrition,
- 11) Unable to provide consent voluntarily due to reasons of capacity or other reasons (e.g. incarcerated, dementia, etc.),
- 12) Unable to complete the study activities for any reason as deemed by the study investigator.

*Additional Inclusion Criteria Aim 1:

- 8) Exposed to GLP-1 agonist treatment in the last 3 years or less, or starting on a GLP-1 agonist in the coming < 3 months,
- 9) Willing to report monthly patient-reported outcomes remotely or in-person.

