Participants will be enrolled for an estimated 72 weeks: Measurements will be requested every four weeks (i.e. q28 days) on a specifically designed survey instrument for MS participants. Participants will be asked to report medication dosing, adherence to medicine, tolerability, weight, height, and exercise activities. Self-reported scales will be administered to the participants as well (measuring disability, fatigue, mood, and quality of life).

Participants must be currently on Ocrelizumab (last dose within the past <6 months) and currently taking a GLP-1 medication.

Participants will be contacted and interviewed via Zoom every 6 months to ensure study procedures are going as planned, verify data reported on medication and MS disease history, and ensure study procedures are operating smoothly. Participants who do not complete the surveys within 7 days of the scheduled timing will be contacted by a study coordinator by phone up to 3 times. Participants will also be asked to report any medication changes, dose changes, or discontinuations if they occur at any point between study visits.

Participants will be enrolled until a total of 40 individual participants are reached. Study procedures for each group are listed in Tables 1 and 2. All scheduled events will be part of the study and not part of routine clinical care.

Table 1: Measurements of MS Participants in Aim 1 (Cohort): Frequency and Scale

Measure	Frequency of Reporting	Scale
Weight	Monthly	kg or lbs
Height	Baseline	cm or inches
Waist, Hip, Limb Circumferences	Monthly	cm or inches
Ambulation score	Monthly	Kurtzke Scale
Disability Score	Monthly	PDSS
Step Count	Monthly	Average daily number on phone or step counter if available
Fatigue	Monthly	Fatigue Severity Scale
Mood	Monthly	Beck Depression Inventory
Quality of Life	q3 months	MS-QOL-54 survey
Intolerabilities	Monthly	Self-reported, qualitative, categorized – gastrointestinal, injection site, infections, etc.
Adherence	Monthly	Number of doses taken/ Total Prescribed doses of GLP-1
Axonal degeneration	Baseline and end of study (if possible)	Neurofilament light chain (serum)
New attacks or lesions	Ad hoc	Reported event if occurs

Table 2: Measurements of MS Participants in Aim 2 (Single-Arm Open-Label Trial)

	Screening	Baseline	Week 24	Week 48	Week 72	Unscheduled Visit (e.g. Relapse, Early Withdrawal)
Clinical & MS Relapse History	X	X	X	X	X	X

Medication Review	X	X	X	X	X	X
Physical Examination	X		X	X	X	X

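### The Aim 2 primary rule counts any threshold EDSS rise as PIRA, with no condition that the participant stayed relapse-free

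*Protocol*

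**What the plan says.** Under Study Endpoints the protocol expands the primary outcome as "progression independent of relapse activity), based primarily on clinical assessment, dichotomized as present or not". The inclusion criteria admit MS "of any type (PPMS, RRMS, SPMS) by a neurologist".

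The Aim 2 analysis text (under Data Management and Confidentiality) then gives the operational rule. A rise of 1.0 points from a baseline below 5.0, or a "positive change in EDSS score of 0.5 points or more with a baseline EDSS score of 5.0 or higher will be considered PIRA". It adds that "the first and last EDSS scores will contribute to the assessment of PIRA for the primary study outcome's hypothesis testing". The last score may come from the planned end of study or from "b) administrative withdrawal, or (c) participant withdrawal".

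For Aim 2, relapse appears elsewhere in three places:
- as an entry exclusion ("Relapse within the past 3 months");
- as a collected background variable covering the year before entry;
- as a Table 2 row ("Clinical & MS Relapse History"), marked at every visit, including the unscheduled visit for which relapse and early withdrawal are the examples. EDSS is also marked at that visit.

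The paragraph before the rule describes the primary outcome "as measured by the rater-determined composite functional outcomes score", built as in the ORATORIO trial. It states no relapse condition.

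**The concern.** The name of the endpoint carries a condition that its scoring rule lacks. An analyst who follows the rule measures threshold EDSS worsening from any cause.

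Relapse-related worsening can enter in two ways. A participant may relapse during follow-up, recover incompletely, and still have a raised EDSS at week 72. Or a participant may leave the study at or soon after a relapse, so that a relapse-affected EDSS becomes the last score. The rule calls both PIRA.

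The sample size justification plans a comparison with a known PIRA proportion and says there is no comparison group. With no concurrent control, extra events from a wider definition do not cancel between arms. They go straight into the estimate and can hide the protection against PIRA that the section on potential benefits hopes to see, or suggest excess progression where there is none.

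**Working it through.** **1. Is the condition stated anywhere?**

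| Place in the protocol | What it says about relapse | Covers baseline to last EDSS? |
|---|---|---|
| Study Endpoints | Expands the acronym; no criterion | No |
| Exclusion criteria | None in the 3 months before entry | No, before baseline |
| Aim 2 variables | Relapse in the year before entry | No, before baseline |
| Table 2 | Relapse history recorded at visits | Recorded, not linked to the rule |
| Aim 2 primary rule | Nothing | No |

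No text excludes, censors or re-baselines a participant after a relapse, or sets a window between a relapse and an EDSS rating.

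**2. The plan's own yardstick.** The sample size justification claims a detectable difference of at least 10 points, with alpha 0.05, power 0.8 and a reference of up to 24%. For one sample against p0 = 0.24 with p1 = 0.14 and n = 40:

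power = Φ{[0.10 − z·√(0.24·0.76/40)] / √(0.14·0.86/40)}

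- Two-sided: (0.10 − 1.96 × 0.0675)/0.0549 = −0.59, power 27.8%.
- One-sided: (0.10 − 1.645 × 0.0675)/0.0549 = −0.20, power 42.0%.

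The stated figure does not reproduce at n = 40. That is a separate issue. The 10 points are used below only as the plan's own scale.

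**3. Effect of each relapse-related case counted as PIRA.** Inputs: 40 participants (Study Aims) and a 10-point difference (sample size justification).

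- One case = 1/40 = 2.5 points, and 2.5/10 = 25% of the planning difference.
- With k cases, a true 10-point reduction appears as 10 − 2.5k points.

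| k | Apparent reduction (points) |
|---|---|
| 1 | 7.5 |
| 2 | 5.0 |
| 3 | 2.5 |
| 4 | 0 |

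**4. How common would that have to be?** Share of participants without true PIRA that cancels the difference = 4 / [40 × (1 − (reference − 0.10))].

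- Reference 24%: 4/(40 × 0.86) = 4/34.4 = 11.6%.
- Reference 20% (assumption): 4/36 = 11.1%.
- Reference 15% (assumption): 4/38 = 10.5%.

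**5. Illustration on the test.** With true PIRA 14% against 24%, two-sided power falls from 27.8% with no such cases to 16.4% with one (16.5% counted) and 9.2% with two (19% counted). With four, the expected count equals the reference.

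**The case against.** The best counter-reading is that the Aim 2 text supplies only the disability threshold and the endpoint's name supplies relapse independence. On that view the two scores only contribute to the assessment, relapse history is collected for this purpose, and the detail may sit in a statistical analysis plan or in the ORATORIO construction. It does not hold. The protocol says outright which changes will be considered PIRA, and an acronym is not a criterion. The trial cited for the composite is described as one in primary progressive MS, whereas this study admits relapsing-remitting patients. An analysis plan that added the condition would depart from the protocol's own rule.

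Several points do stand:
- All participants are ocrelizumab-treated at enrolment and recent relapse is excluded at entry, so the number of affected cases could be small or zero.
- The withdrawal route is narrow, because participants who stop the GLP-1 agonist are still followed to week 72. Residual relapse disability at week 72 is the broader route.
- A relapse-free condition has its own bias. A participant who truly progressed and also relapsed moves out of the PIRA count, which lowers the proportion and favours a protective reading. Both counts therefore need to be reported.
- The protocol gives no definition of a relapse and the investigators are not blinded to the outcome, so a rule that turns on a recorded relapse needs that term fixed.

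**Conclusion.** The concern holds, and the rule must be corrected. As written, it does not measure the endpoint it is named for. Against a relapse-free definition the error runs one way: it raises the counted proportion. Each case is worth 2.5 points in 40, and four cases equal the whole planning difference. These figures follow from the sample size of 40 and the 10-point difference alone. They show sensitivity, not expected bias, which cannot be derived without an on-study relapse rate. The gap in the wording is certain; its effect on the result is not known.

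**What to change.** Amend the Aim 2 primary rule so that a threshold EDSS rise counts as PIRA only if no relapse is recorded from baseline up to and including the visit of the last EDSS score. With it:

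- Keep all participants in the denominator.
- Report threshold rises with a recorded relapse as a separate category, relapse-associated worsening.
- Report the count under the present wording beside the primary count as an upper bound, so that participants who both progressed and relapsed stay visible.
- State what counts as a recorded relapse.
- State whether the EDSS rise alone decides the primary test or is one limb of the composite. If the composite decides, the relapse condition has to apply to its other components too.
- Write the lower limb as a rise of 1.0 points or more.
- Optionally, add a sensitivity analysis limited to rises still present at the next scheduled visit.

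The cost is protocol wording and an extra line in the results table. EDSS and relapse history are already scheduled at baseline, weeks 24, 48 and 72 and at unscheduled visits. The price is somewhat fewer primary events, and true progressors who also relapsed, even with full recovery, are reported as relapse-associated. The upper-bound count shows how many participants this affects.
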